## 7 PLANNED ANALYSES

Disposition of the patient population participating in the trial, the overall disposition information and the disposition status will be analysed by treatment grouping 1 and 6 separately. Disposition of the patients after re-randomisation of the initial placebo group will be analysed by TG7 and after re-randomisation of the initial empagliflozin group will be analysed by TG4. They will be presented in the clinical trial report as a frequency-distribution.

The number of patients participating (screened, randomised, treated, and prematurely discontinued treatment) in the study by region and country will also be analysed and presented as a frequency distribution. The primary reason for patients failing screening will also be summarised. See [Table 9.1: 1](#) for assignment of countries within region.

In addition, the following analyses will be done for public data disclosure on European Union Drug Regulating Authorities Clinical Trials (EudraCT) and display in Appendix 16.1.13 for both DINAMO and DINAMO Mono together.

- Disposition of patients, including number of patients who discontinued trial medication due to fatal and non-fatal adverse events, by TG8 based on RS
- Number of screened patients by country based on SCR
- Number of screened patients by age (at time of informed consent) groups (Children (2-11 years), Adolescents (12-17 years)) based on SCR

A summary of the number of patients in each randomisation stratum per treatment for each of the 3 randomisations (i.e. Day 1, Week 14 and Week 26) will also be shown. These summaries will be based upon the data received from the IRT provider.

An IPD table will be presented including all CTP deviations leading to exclusion from analysis set (PPS, mITT, TS and/or TSactive) and an additional IPD table will be created to summarise all the IPDs not leading to exclusion from an analysis set using treatment grouping 1 based on RS.

For in-text tables presenting descriptive analysis of the endpoints and other variables, the set of summary statistics is: N (number of patients with non-missing values), mean, standard deviation (SD).

For End-Of-Text tables, the set of summary statistics is: N (number of patients with non-missing values) / Mean / SD / standard error (SE) / Min / Q1 (lower quartile) / Median / Q3 (upper quartile) / Max.

Statistical parameters will be displayed to a defined number of decimal places as specified in the BI guideline “Reporting of Clinical Trials and Project Summaries” (4). Figures will be added if deemed necessary.

HbA1c and FPG in conventional unit will be analysed in Appendix 15.2 and SI unit will be analysed in Appendix 16.1.13.1. All analyses of laboratory parameters with SI unit will be analysed in Appendix 15 and the analyses of laboratory parameters with conventional unit will be analysed in Appendix 16.1.13.1.

Tabulations of frequencies for categorical data will include all possible categories and will display the number of observations in a category as well as the percentage (%) relative to the respective treatment group (unless otherwise specified, all patients in the respective patient set whether they have non-missing values or not). Percentages will be rounded to one decimal place. The category missing will be displayed only if there are actually missing values.

The following analyses will be performed to assess the impact of COVID-19.

- Premature discontinuation of trial medication or study due to COVID-19 disruption, by TG1 on SCR
- Patients screened and study conduct (assessed HbA1c at Week 26 (regardless on or post-treatment), last intake of study medication, completed study participation) relative to start of COVID-19 disruption by before and from start of COVID-19 disruption on SCR
- Number of patients with protocol deviations associated with COVID-19 disruption, by TG1 on RS
- Listing of patients with COVID-19 related study disruption on SCR

All described outputs, except result disclosure outputs, will be presented separately for DINAMO and DINAMO mono.

All result disclosure outputs will be presented in the final reporting only at the same time as DINAMO Mono reporting.

## 7.1 DEMOGRAPHICS AND OTHER BASELINE CHARACTERISTICS

### 7.1.1 Baseline evaluation

Descriptive analysis of the following demographic variables measured at study baseline will be presented:

Sex, race, ethnicity, region, age [years] at informed consent (continuous), age [years] at randomisation (categories), BMI [kg/m^2] (continuous and categories), BMI z-score (continuous and categories), height [cm], height z-score, smoking history, time since diagnosis of diabetes [years] (categories), eGFR [mL/min/1.73m^2] (Zappitelli) (continuous and categories) and Tanner stages.

See [Section 7.8.2.4](#) for details on the derivation of eGFR endpoints.

Descriptive analysis of the following variables measured at study baseline will be presented:

HbA1c [%] (continuous and categories), FPG [mg/dL] (continuous and categories), FPG [mmol/L] (continuous and categories), weight [kg] (continuous and categories), blood pressure [mmHg] (categories), fasting C-peptide [nmol/L], UACR [mg/g crea] (continuous and categories).

Categories for baseline characteristics are defined in [Table 6.4: 1](#).

Demographic and baseline characteristics tables will be presented using the TS by treatment grouping 1.

The demographic analysis will be repeated on the randomised set by TG8 in Appendix 16.1.13 for disclosure on EudraCT for both DINAMO and DINAMO Mono together.

The following analyses will be performed to assess the impact of COVID-19 for DINAMO only.

- Demographic data by patients randomised before and from the start of COVID-19 disruption, by TG1 based on TS
- Baseline efficacy variables by patients randomised before and from the start of COVID-19 disruption, by TG1 based on TS

## 7.2 CONCOMITANT DISEASES AND MEDICATION

Only descriptive statistics are planned for this section of the report using the TS and TSactive accordingly.

Concomitant therapy use will be summarised by Anatomical-Therapeutic-Chemical classification level 3 (ATC3) and preferred name. Only therapies under their available ATC3 code(s) will be presented. Summaries will be presented for concomitant therapies taken during randomised treatment which are newly initiated (i.e. new preferred name) during the dedicated randomised treatment period and those taken at baseline (i.e. on day 1) of the dedicated randomised treatment period.

The summary on concomitant therapies during randomised treatment will be presented up to Week 26 by treatment grouping 1 and Week 52 by treatment grouping 6.

Separate summary of use of antihypertensives, ASA, or lipid lowering drugs at baseline will be presented by TG1 and during randomised treatment will be presented up to Week 26 by treatment grouping 1 and Week 52 by treatment grouping 6. The displayed categories and defining ATC levels and ATC codes are shown in [Section 9.2](#).

Concomitant diagnoses and non-drug therapies at any time of the study will be summarised by Medical Dictionary for Regulatory Activities (MedDRA) System Organ Class (SOC) and preferred term (PT). Relevant diabetic medical history will also be presented by treatment grouping 1.

Background antidiabetic treatment at baseline (i.e. on day 1) will be summarised for the DINAMO patients only by treatment grouping 1 presenting number of background antidiabetic treatments (0, 1, 2), background antidiabetic treatment (metformin only, insulin only, metformin and insulin, none (diet and exercise only, metformin not tolerated)), metformin total daily dose [mg] (continuous and categories), and basal insulin total daily dose [IU/day].

Antidiabetic medication newly introduced on treatment will be presented up to Week 26 by treatment grouping 1 and Week 52 by treatment grouping 5. The increase dose of insulin during the on-treatment period is not included in this presentation for the DINAMO patients but it will be presented in the “initiate glycaemic rescue therapy” further efficacy endpoint. The antidiabetic medication newly introduced on treatment will be regarded as rescue medication for the DINAMO Mono patients.

### 7.3 TREATMENT COMPLIANCE

Only descriptive statistics are planned for this section of the report.

Descriptive summary of compliance [%] and frequency distribution of patients with compliance [%] in categories (< 75, 75 to 125, > 125, incalculable (i.e. Not collectable compliance with reason for missing compliance)) will be reported by visit and treatment grouping 1 and 6 using TS and TSactive. Post-treatment period will not be included in the compliance analysis. In case of premature discontinuation of treatment up to Week 26 for the TG1 summary table, premature discontinuation visit or Visit 8/End of treatment compliance will be presented together as ‘PTD prior to Week 26’. For up to Week 52 TG6 summary table, all end of treatment visits including premature discontinuation of treatment will be presented together as ‘Visit 8/EOT’.

The following analyses will be provided to assess the impact of COVID-19 for DINAMO only.

- Compliance data over time up to Week 26 by visit and permanent discontinuation of study medication or/and completion of Week 26 visit before/from the start of COVID-19 disruption, by TG1 on TS.
- Compliance data over time up to Week 52 by visit and permanent discontinuation of study medication before and from the start of COVID-19 disruption, by TG6 on TSactive.
- Compliance with study medication before and from the start of COVID-19 disruption by visit on TS
- Frequency of patients and rate of treatment interruptions up to Week 26 before and from the start of COVID-19 disruption by TG1 on TS. The time at risk is the entire treatment duration. The time at risk for the period before start of COVID-19 disruption is defined as first dose of treatment until either the day before COVID-19 start date or treatment end date (whichever comes earlier). The time at risk for the

period from start of COVID-19 disruption is defined as COVID-19 start date or treatment start date (whichever comes later) until treatment end date. Treatment interruptions which started during the defined period will be counted toward that specific defined period.

## 7.4 PRIMARY ENDPOINTS

### 7.4.1 DINAMO

The primary endpoint in this trial is the change in HbA1c [%] from baseline to the end of 26 weeks.

#### 7.4.1.1 Primary family of analyses

The primary family of null hypotheses will be tested using alpha level of 5% (two-sided):

For empagliflozin, the following null hypothesis will be tested:

$H_{0,1}$ : Mean change in HbA1c [%] from baseline to the end of 26 weeks in the pooled empagliflozin groups  
= Mean change in HbA1c [%] from baseline to the end of 26 weeks in the placebo group

For linagliptin, the following null hypothesis will be tested:

$H_{0,2}$ : Mean change in HbA1c [%] from baseline to the end of 26 weeks in the linagliptin 5 mg group  
= Mean change in HbA1c [%] from baseline to the end of 26 weeks in the placebo group

These confirmatory primary analyses will be performed using an effectiveness “wash-out” approach based on the mITT (OC-AD) set with multiplicity adjustment for simultaneous testing of linagliptin and empagliflozin using the Hochberg procedure by treatment grouping 1. Patients will be assigned to the treatment they were randomised to at the initial randomisation. All randomised treatment groups will be included in the same analysis. The seed used in the DINAMO confirmatory analyses will be 1218009101.

HbA1c values measured after premature discontinuation of study drug or after rescue therapy was initiated will be included in the analyses. All available on- and off-treatment data up to the Week 26 time point will be included.

There will be different types of missing data to be considered for the imputation.

Table 7.4.1.1: 1 “Wash-out” approach – the missing data imputation method

**Randomised treatment group: Placebo**

Missing HbA1c data will be imputed for all scheduled visits up to Week 26, that includes Week 4, Week 12 and Week 26.

Type of missing data	Data used for imputation	Method to use for	
		Non-monotone missing data	Monotone missing data
On- and off-treatment data	Observed on- and off-treatment HbA1c data in the placebo group, including Baseline, Week 4, Week 12 and Week 26.	MCMC-MI  (MAR  )	SLR-MI  (MAR  )

**Randomised treatment groups: Linagliptin 5 mg and empagliflozin pooled**

Missing HbA1c data will be imputed for Week 26 only.

Type of missing data	Data used for imputation	Method
On-treatment data	Observed on-treatment HbA1c data in the respective treatment group, including only Baseline and Week 26.	SLR-MI  (MAR  )
Off-treatment  data	Observed on- and off-treatment  HbA1c data in the placebo group, including only Baseline and Week 26.	SLR-MI  (MNAR  )

 Markov Chain Monte Carlo – Multiple imputation (MCMC-MI)

 Sequential linear regression – Multiple imputation (SLR-MI)

 Missing at random (MAR)

 Missing not at random (MNAR)

 Missing post-treatment data after permanent treatment discontinuation

**Method of imputation**

For the placebo group, missing HbA1c data, regardless on- or off-treatment, will be imputed for all scheduled visits up to Week 26.

\* The non-monotone missing data will be imputed using Markov Chain Monte Carlo (MCMC) simulation and standard techniques; MI will be performed on a data set including on- and off-treatment HbA1c data in the placebo group at baseline, Week 4, Week 12 and Week 26 with baseline HbA1c as a continuous covariate and age at randomisation as binary covariate corresponding to its class categorisation levels (age <15 years or age ≥15 to <18 years). 500 imputations will be performed to ensure adequate efficiency and stability of the estimation for missing data. This step will be referred to as ‘MCMC-MI’.

\* For the monotone missing data in the placebo group, a sequential linear regression MI approach will be used and referred to as ‘SLR-MI’. The MI will be performed on a data set

including on- and off-treatment data and once per imputation from the previous step. This procedure will impute values for all missing time points both on- and off-treatment. The regression models will be fitted with baseline HbA1c as a continuous covariate and age at randomisation as a binary covariate (age <15 years or age  $\geq$ 15 to <18 years). 500 imputations for the placebo group will be completed.

For the active treatment groups (linagliptin 5 mg and empagliflozin pooled, regardless of the dose level), missing HbA1c data will be imputed for Week 26 only separately for missing on-treatment data and missing off-treatment data.

\* To impute the missing on-treatment data at Week 26, the MI will be performed on a data set including only patients who were on active treatment at Week 26, using the baseline and Week 26 (both missing and non-missing values). The regression models will be fitted separately by active treatment group with baseline HbA1c as a continuous covariate and age at randomisation as a binary covariate (age <15 years or age  $\geq$ 15 to <18 years). 500 imputations for missing on-treatment data in each active treatment group will be completed.

\* To impute the missing off-treatment data at Week 26, the MI will be performed on a data set including the baseline of the active treated patients with missing off-treatment HbA1c data at Week 26, and the placebo patients with baseline and the original (i.e. not imputed) on- and off-treatment HbA1c data from Week 26. The regression models will be fitted separately by active treatment group with baseline HbA1c as a continuous covariate and age at randomisation as a binary covariate (age <15 years or age  $\geq$ 15 to <18 years). 500 imputations for missing off-treatment data in each active treatment group will be completed.

The effectiveness analyses will be performed on these imputed data sets plus the observed HbA1c data at Week 26 using an ANCOVA model with baseline HbA1c as a continuous model term, and with categorical terms for treatment and age at randomisation. Rubin's rules will be used to combine treatment estimates across the 500 complete imputations.

The implicit assumption underlying the imputations and analyses is that unobserved off-treatment patient measurements will lose any treatment effect immediately off-treatment discontinuation in the active treatment groups.

The least square mean differences of the active treatments to placebo, confidence intervals and p-values of change in HbA1c from baseline to the end of 26 weeks will be displayed via forest plots for the primary (primary family of hypotheses) and corresponding sensitivity analyses, refer to [Section 7.4.1.3](#), separately for linagliptin and empagliflozin pooled.

A more technical description of the method can be found in [Section 9.4](#).

#### 7.4.1.2 Secondary family of analyses

After having obtained statistically significant results for both hypotheses  $H_{0,1}$  and  $H_{0,2}$  of the primary family of hypotheses in the effectiveness “wash-out” approach analysis, the following two hypotheses will be tested in a hierarchical order at significance level  $\alpha=0.05$  (two-sided) for the comparison of empagliflozin versus placebo:

H'0,1: Mean change in HbA1c [%] from baseline to the end of 26 weeks in regimen starting on empagliflozin 10 mg and either having a dose increase to empagliflozin 25 mg in patients who were non-responders (i.e. patients that did not achieve HbA1c < 7.0%) at Week 12, or who were responders (i.e. patients that did achieve HbA1c < 7.0%) at Week 12 and continue with empagliflozin 10 mg  
= Mean change in HbA1c [%] from baseline to the end of 26 weeks in the placebo group.

followed by:

H'0,2: Mean change in HbA1c [%] from baseline to the end of 26 weeks in regimen starting on empagliflozin 10 mg and either were responders or were non-responders at Week 12, and continue with empagliflozin 10 mg  
= Mean change in HbA1c [%] from baseline to the end of 26 weeks in the placebo group.

The hypotheses H'0,1 (by treatment grouping 2) will be tested first and if this hypothesis can be rejected at the significance level  $\alpha = 0.05$ , the hypotheses H'0,2 (by treatment grouping 3) will be tested at the same level. The empagliflozin 10 mg patients who did not proceed to re-randomisation at Week 14 will also be included in the analysis.

In using two sets of hypotheses families in a hierarchical order and using all hypotheses in the primary family as a gatekeeper for the secondary family, the experiment wise Type I error rate across both families is controlled by the significance level  $\alpha = 0.05$ .

These secondary family of hypotheses for the primary endpoint will be tested using the “wash-out” approach described in [Section 7.4.1.1](#) but the ANCOVA used for analysis of the completely imputed set will apply an “inverse probability weighting” approach based on the mITT (OC-AD) set.

The ANCOVA models will utilise a weight having a value of 0 for the patients who are not in the hypothesis test of interest; a value of 2 for re-randomised patients who are in the hypothesis test of interest and a value of 1 otherwise. The model terms will include baseline HbA1c as a continuous variable, and treatment and age at randomisation as categorical variables. Rubin’s rules will be used to combine treatment estimates across the 500 imputations.

Patients will be assigned to the treatment they were randomised to at the initial randomisation together with the treatment allocation at Week 14 randomisation. HbA1c values measured after premature discontinuation of study drug or after rescue therapy was initiated will be included in the analyses. Patients discontinued from the randomised study medication prior to Week 15 will also be included in the analysis.

The least square mean differences for each of the empagliflozin doses versus placebo, confidence intervals and p-values of change in HbA1c from baseline to the end of 26 weeks

[figure not shown]
will be displayed via forest plots for the analyses of the secondary family of hypotheses and corresponding sensitivity analyses, refer to [Section 7.4.1.3](#), separately for TG2 and TG3.

[figure not shown]

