4.1.3 Method of assigning patients to treatment groups

During Visit 2, eligible patients will be randomised to receive either linagliptin 5 mg or empagliflozin 10 mg or placebo in a 1:1:1 ratio according to a randomisation plan. The assignment will occur in a blinded fashion via Interactive Response Technology (IRT).

At Visit 4B, patients assigned to the empagliflozin group who do not achieve an HbA1c value < 7% at Week 12 will be re-randomised to receive either empagliflozin 10 mg or empagliflozin 25 mg in a 1:1 ratio. The assignment will occur in a blinded fashion via Interactive Response Technology (IRT).

At Visit 5, patients assigned to the placebo group will be re-randomised to receive either linagliptin 5 mg or empagliflozin 10 mg or empagliflozin 25 mg in a 1:1:1 ratio according to a randomisation plan. The assignment will occur in a blinded fashion via IRT.

To ensure double-blind conduct, investigators will have to perform an IRT call for all patients at Week 14 (Visit 4B) and Week 26 (Visit 5).

Access to the codes will be controlled and documented. Technical and statistical features of the process of treatment allocation are described in [Section 7.6](#).

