7.3.1.1.2 Analysis of the secondary family of hypotheses

If the “wash-out” approach analysis for both hypotheses in the primary family of hypotheses shows a statistically significant result, the secondary family of hypotheses will be tested as ordered hypotheses at the significance level $\alpha = 0.05$ (two-sided), i.e., the hypotheses $H'_{0,1}$ will be tested first and if this hypothesis can be rejected at the level $\alpha = 0.05$, the hypotheses $H'_{0,2}$ will be tested at the same level.

In using two sets of hypotheses families in a hierarchical order and using all hypotheses in the primary family as a gatekeeper for the secondary family, the experimentwise Type I error rate across both families is controlled by the significance level $\alpha = 0.05$.

These secondary family of hypotheses for the primary endpoint will be tested using the “wash-out” approach described in [Section 7.3.1.1](#) but the ANCOVA used for analysis of the completely imputed set will apply an “inverse probability weighting” approach based on the mITT set.

The ANCOVA model will utilise a weight variable having a value of 0 for the patients who are not in the hypothesis test of interest; a value of 2 for re-randomised patients who are in the hypothesis test of interest and a value of 1 otherwise. The model terms will include baseline HbA1c as a continuous variable, and treatment and age as categorical variables. Rubin’s rules will be used to combine treatment estimates across the 500 imputations.

Patients will be assigned to the treatment they were randomised to at the initial randomisation together with the treatment allocation at Week 14 randomisation. HbA1c values measured after premature discontinuation of study drug or after rescue therapy was initiated will be included in the analyses. All data up to the Week 26 time point will be included.

The treatment comparisons for $H'_{0,1}$ and $H'_{0,2}$ according to [Section 7.2.2](#) are as follows:

For $H'_{0,1}$, this is a contrast between patients who started empagliflozin 10 mg and either having a dose increase in patients who were non-responder at Week 12, or who were responders at Week 12 and continue with empagliflozin 10 mg, and placebo.

For $H'_{0,2}$, this is a contrast between patients who started empagliflozin 10 mg and either were responders or were non-responders at Week 12 and continue with empagliflozin 10 mg, and placebo.

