Studies 1218.17, 1218.36 and 1245.23 assessed the change from baseline to Week 24 as primary endpoint, in studies 1245.33 and 1245.49 the primary endpoint was change from baseline to Week 18. For all calculations raw means and standard deviations for the primary endpoint were considered as initial basis for further calculations.

Table 7.7.1: 1 HbA1c (%) change from baseline to Week 18 or 24 for studies with T2DM patients treated with linagliptin or empagliflozin

Study number	Placebo			Active treatment				Corrected treatment difference ⁴
	N	Mean ¹	SD ²	N	Mean ¹	SD ²	N disc. ³	Mean Active - Placebo
1218.17 - Week 24 linagliptin 5 mg	156	-0.07	1.03	471	-0.66	0.85	39	-0.54
1218.36 - Week 24 linagliptin 5 mg	560	0.01	0.93	568	-0.66	0.89	36	-0.63
1245.23 – Week 24 empagliflozin 10 mg	183	-0.26	0.79	206	-0.76	0.76	8	-0.48
1245.33 – Week 18 empagliflozin 10 mg	145	0.06	0.89	152	-0.69	0.88	16	-0.68
1245.49 – Week 18 empagliflozin 10 mg	173	-0.59	0.85	170	-1.04	0.79	17 ^a	-0.41

¹ Mean change from baseline in HbA1c at Week 18 or 24 based on the observed means in the raw data (including post rescue medication data)

² Observed standard deviation in the raw data up to Week 18 or 24 (including post rescue medication data)

³ Number of patients prematurely discontinuing active treatment prior to endpoint visit according to report disposition table

⁴ Assuming placebo response for patients prematurely discontinuing active treatment

^a Number of patients excluded from full analysis completers set, estimate of treatment discontinuations up to Week 18

Based on these results a mean treatment difference in HbA1c change from baseline of -0.55% with a SD of 0.9% between active drugs and placebo can be assumed. For the effectiveness analysis a covariate adjusted standard deviation of 0.9% can be regarded as the expected scenario, while 0.8% will probably be optimistic. A conservative scenario of 1.0% is added because of the potential of increased variability through the multiple imputations performed for the “wash out”. Power estimates in [Table 7.7.1: 2](#) are based on a two-sided t-test at alpha-level of 0.05. Additionally the power is given for the alpha-level of 0.025 to provide a lower bound of the expected power due to the Hochberg correction for multiplicity.

Table 7.7.1: 2 Power estimates for various scenarios for the “wash out” effectiveness analysis

Alpha (2-sided)	Treatment effect (%)	Covariate-adjusted standard deviation (%)	Sample size per group	Power

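### Does the weighted ANCOVA for the two empagliflozin regimen tests need a named variance estimator?

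*SAP*

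**What the plan says.** H'0,1 (start on 10 mg, increase in Week 12 non-responders) and H'0,2 (stay on 10 mg throughout) are tested in order, each against placebo at two-sided 5%, and only if both primary hypotheses are rejected.

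Protocol 7.3.1.1.2 says the ANCOVA "will utilise a weight variable having a value of 0 for the patients who are not in the hypothesis test" of interest, and SAP 7.4.1.2 repeats the scheme: 0 for patients outside the test, then "a value of 2 for re-randomised patients who are in the hypothesis test of interest and a value of 1 otherwise". The covariates are fixed: "The model terms will include baseline HbA1c as a continuous variable, and treatment and age at randomisation as categorical variables". Estimates from 500 imputations are combined by Rubin's rules.

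The 2 comes from the design. Protocol 4.1.3 says Week 12 non-responders on empagliflozin "will be re-randomised to receive either empagliflozin 10 mg or empagliflozin 25 mg in a 1:1 ratio", so each has probability one half of staying in a given regimen.

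Neither section says how the standard error of the weighted estimate is computed. SAP 7.4.1.2 does say that the wash-out approach of 7.4.1.1 applies, and 7.4.1.1 closes with: "A more technical description of the method can be found in" Section 9.4. That section is not in the text available.

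**The concern.** An inverse-probability weight of 2 means that one patient stands in for two. Weighted least squares with its usual standard error reads the 2 differently, as if that patient's outcome had half the variance. The weighted residual variance rises and repairs part of the error, but not all of it.

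Rubin's rules need a within-imputation variance, so an ingredient of two confirmatory tests looks to be left open. The results will also be shown: the SAP promises forest plots with "The least square mean differences for each of the empagliflozin doses versus placebo, confidence intervals and p-values" for this family. If the standard error were too small, the local tests would run above 5% and the 95% intervals would be too narrow. The unweighted primary comparisons are untouched.

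**Working it through.** **Inputs.** From Protocol 7.7.1: 50 patients per arm, effect -0.55, SD 0.9. From Protocol 4.1.3: 1:1 re-randomisation. Assumed: q, the share of the empagliflozin arm that is re-randomised, from 0.3 to 1.0. The nearest figure in the documents is in Protocol 1.2.2: 36.4% of patients on linagliptin 5 mg with baseline HbA1c of at least 7% reached target in the earlier paediatric trial, which would suggest q near 0.64.

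**The plan's own figure.** A two-sample t-test with 50 per arm, effect 0.55 and SD 0.9 gives 85.7% power at 5% and 78.1% at 2.5%. Protocol Table 7.7.1: 2 states 85% and 78%. The documents give no power or standard error for the weighted tests.

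**Closed form (complete data, common SD, no covariates).** The regimen arm has 50(1-q) patients at weight 1 and 25q at weight 2. The weights sum to 50 and their squares to 50(1+q).

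- True variance of the difference: SD²[1/50 + (1+q)/50] = SD²(2+q)/50.
- Expected weighted residual sum of squares: SD²[49 + 50 - (1+q)] = SD²(98-q), on 98-25q degrees of freedom when weight-0 patients are left out.
- Expected default variance: SD² × (98-q)/(98-25q) × 2/50.
- SE ratio, default over true: √{2(98-q)/[(98-25q)(2+q)]}.

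| q | true SE | default SE | ratio | local type I error |
|---|---|---|---|---|
| 0.3 | 0.193 | 0.187 | 0.969 | 5.7% |
| 0.6 | 0.205 | 0.195 | 0.950 | 6.2% |
| 0.64 | 0.207 | 0.196 | 0.948 | 6.3% |
| 0.9 | 0.217 | 0.204 | 0.942 | 6.5% |
| 1.0 | 0.220 | 0.207 | 0.941 | 6.5% |

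Example, q = 0.6: 2 × 97.4/(83 × 2.6) = 0.903, with square root 0.950.

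**Simulation with baseline and age as covariates, complete data.** In one set of runs (20,000 per scenario, q from 0.34 to 0.88) the default SE was 2.8% to 6.6% too small, with type I error 5.6% to 6.5% and coverage 93.5% to 94.5%. The HC2 sandwich gave 4.8% to 5.3%. So the mechanism is real when nothing is missing.

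**The same test with imputation.** Under SAP 7.4.1.1, missing Week 26 values after permanent discontinuation of active drug are drawn from the placebo regression. This draws the regimen arm towards placebo while Rubin's rules keep a full variance. Two sets of runs, both imputing all missing values from placebo, gave these type I error rates:

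| share missing | default, set 1 | HC2, set 1 | default, set 2 | HC2, set 2 |
|---|---|---|---|---|
| 2% | 5.7% | 4.9% | 5.3% | 4.5% |
| 4% | 5.0% | 4.1% | – | – |
| 5% | – | – | 4.6% | 3.7% |
| 6% | 4.2% | 3.6% | – | – |
| 10% | 3.6% | 3.1% | 3.6% | 3.0% |

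The default crosses the nominal level at about 4% missing. Protocol Table 7.7.1: 1 gives the "Number of patients prematurely discontinuing active treatment prior to endpoint visit according to report disposition table" for most of the planning studies, and an estimate to Week 18 for one: 8/206 = 3.9%, 36/568 = 6.3%, 39/471 = 8.3%, 17/170 = 10.0%, 16/152 = 10.5%. Off-treatment follow-up may keep the missing share below these rates.

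**The gate.** With both primary tests required first (8,000 complete-data runs per case, default errors), false rejection of H'0,2 was 3.1% and 3.5% for 25 mg effects of -0.9 and -1.5. For H'0,1 it was 2.0% with empagliflozin null and linagliptin at -0.55. Local rates in the same runs were 5.8% to 6.2%.

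**Cost of a switch to HC2.** Intervals are 3% to 6% wider, and power for H'0,1 at -0.55 falls from 78%–79% to 75%–77%.

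**The case for a change.** The best case for acting is that these are the only confirmatory tests of the individual empagliflozin regimens, and that reasonable choices give different p-values. Gating limits false rejection but does not widen an interval that is too narrow. If weight-0 patients were counted in the residual degrees of freedom, the standard error would be 7% to 19% too small. If non-responders were more variable than responders (SD 1.0 to 1.2 against 0.6 to 0.7, not in the documents), complete-data type I error would be 6.6% to 8.0%. The remedy is one sentence, and the SAP is otherwise precise: it fixes the imputation seed and names Kenward-Roger for the repeated-measures models.

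Part of this stands. The visible text is silent, and with almost complete data an interval from default errors would be slightly too narrow. The imputation runs also draw every missing value from placebo, whereas the plan imputes missing on-treatment values from the patient's own arm; the offset depends on the off-treatment share.

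The rest is weaker. SAP treatment groupings 2 and 3 list only the patients in each comparison, so leaving the others out of the degrees of freedom is the plain reading. No sandwich variant is right at every missing share: HC2 is nearer nominal at 2% missing in set 1, but further away than the default from 5% upwards. And the estimator may be stated in Section 9.4.

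**Conclusion.** No change follows. If default errors were used and almost no Week 26 values were missing, the standard error would be about 3% to 6% too small under equal SDs, with local type I error of about 5.7% to 6.5%. This rests on an assumed q of 0.3 to 1.0. Once about 4% or more of the values are imputed from placebo, the default test is at or below its nominal level, and the planning studies' discontinuation of 3.9% to 10.5% makes that share plausible, though not certain. The experimentwise 5% is not shown to fail; the gated rates were 2.0% to 3.5%.

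What remains is a detail that Section 9.4 may already supply, and that a competent analyst would settle without harm to the conclusions. Prescribing HC2 would exchange a small possible excess under near-complete data for more conservatism and some lost power otherwise, in a trial whose size was held down to limit the exposure of children. That is a fair trade-off to leave as it is. An analyst could report a sandwich interval as a sensitivity analysis, but the plan does not need it.
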